8.2.2.8. Overall Response Rate (ORR)

The ORR is defined as the percentage of subjects with BOR of sCR, CR, VGPR, or PR relative to the appropriate analysis set.

Criteria for IMWG Response as specified in Appendix 2 and 3. A response can be confirmed with a second response of same or better.

This is calculated from a sequence of objective status evaluations. The mITT analysis set and response evaluable analysis set will be used.

Table 6. Criteria for Best Response

sCR [#]	Stringent Complete Response: An objective status of Stringent Complete Response on at least two sequential disease assessments.
CR [#]	Complete Response: An objective status of Complete Response on at least two sequential disease assessments.
VGPR	Very Good Partial Response: An objective status of Very Good Partial Response on at least two sequential disease assessments.
PR	Partial Response: An objective status of Partial Response on at least two sequential disease assessments.
MR	Minimal response: An objective status of Minimal Response on at least two sequential disease assessments.
UsCR	Unconfirmed sCR: One objective status of Stringent Complete Response (based on evidence from serum and urine studies and, if drawn, bone marrow biopsy) but the confirmation studies are either not done, or when done, do not meet the requirements necessary to confirm response. This must be documented before progression and before new anti-cancer therapy.
UCR	Unconfirmed CR: One objective status of Complete Response (based on evidence from serum and urine studies and, if drawn, bone marrow biopsy) but the confirmation studies are either not done, or when done, do not meet the requirements necessary to confirm response. This must be documented before progression and before new anti-cancer therapy.
UVGPR	Unconfirmed VGPR: One objective status of Very Good Partial Response, but the confirmation studies are either not done, or when done, do not meet the requirements necessary to confirm response. This must be documented before progression and before new anti-cancer therapy.
UPR	Unconfirmed PR: One objective status of Partial Response, but the confirmation studies are either not done, or when done, do not meet the requirements necessary to confirm response. This must be documented before

Table 6. Criteria for Best Response

	progression and before new anti-cancer therapy.
SD	No Change/Stable Disease: At least one objective status of Stable Disease but not qualifying as any of the above. If radiographic studies were performed there should be no known progressive or new bone lesions. Subjects who had a single response of sCR, CR, VGPR, PR, or MR but no SD response can also confirm SD.
Progressive Disease (PD)	First objective status recoded of Progression. Progression is defined per the IMWG response criteria for Progressive Disease. Clinical relapse will be equivalent to PD. Note that a progression is defined as: 
 • 2 consecutive assessments of PD, • or 1 PD as last efficacy assessment followed by permanent treatment discontinuation, • or 1 PD following treatment discontinuation (EOT for both treatments in combined therapy - Part 1C and Part 1D). If the discontinuation is after PD but before the next response, then it is considered PD. If there are better responses before discontinuation, it is not considered PD to allow for possible pseudo progression from the treatment which is clinically possible and accepted.

CR and sCR: MRD tests should be initiated only at the time of suspected complete response. Confirmation with two consecutive assessments is not required.

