1.2.3.2. Efficacy

Clinical activity has been observed in Study C1071001. As of the 22 June 2022 data cutoff date, the confirmed objective response rate at the full 1000 µg/kg or 76 mg [QW or Q2W dosing regimen (N=41)] was 63.4% (95% CI, 48.1, 76.4), per IMWG criteria. Responses were durable and deepened over time. Median duration of follow-up for all 41 patients treated at the full 1000 µg/kg or 76 mg (QW or Q2W dosing regimen) was 10.94 months (0.30, 24.41). For responding participants, the median duration of response (95% CI) was 11.6 (7.2, NE) months. The median progression-free survival (95% CI) was 10.4 (4.7, 15.2) months.

Additional information for this compound may be found in the single reference safety document (SRSD), which for this study is the Investigator's Brochure.

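### SAP 8.2.2.8 gives two inconsistent rules for confirming a response: the text accepts the same or a better category, while Table 6 asks for the identical category twice

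*SAP*

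**What the plan says.** SAP 8.2.2.8 builds the response rate on best overall response: "The ORR is defined as the percentage of subjects with BOR of sCR, CR, VGPR, or PR relative to the appropriate analysis set". Protocol 9.4 and SAP 2.2.1 count confirmed responses only.

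The general rule for confirmation is one sentence above Table 6: "A response can be confirmed with a second response of same or better".

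Table 6 then defines each confirmed category separately. For PR it is "An objective status of Partial Response on at least two sequential disease assessments"; for VGPR, "An objective status of Very Good Partial Response on at least two sequential disease assessments"; for CR, "An objective status of Complete Response on at least two sequential disease assessments". The sCR and MR rows follow the same pattern. None of the five allows a better category at the second assessment.

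Unconfirmed categories follow for sCR, CR, VGPR and PR. The PR version reads "One objective status of Partial Response, but the confirmation studies are either not done, or when done, do not meet the requirements necessary to confirm" the response. These rows do not restate what the requirements are. The stable disease row adds: "Subjects who had a single response of sCR, CR, VGPR, PR, or MR but no SD response can also confirm SD".

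Appendix 2 in both documents asks for two consecutive assessments for every response category but does not say whether the second may be better. No passage ranks the sentence above the table or the table above the sentence.

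The date of first confirmed response is used elsewhere. SAP 8.2.2.3 ends TTR, and SAP 8.2.2.6 starts DoR, at the first documented response that is later confirmed.

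**The concern.** Under the sentence, a PR followed by a VGPR is a confirmed PR. Under the PR row read on its own, it is not, because PR occurs once. The two rules therefore part for patients who keep improving, and protocol 1.2.3.2 says of this drug: "Responses were durable and deepened over time".

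Two things are at stake. First, a patient whose category rises at each visit and never repeats could be left out of ORR and CBR. The stable disease row could even let such a patient be recorded as stable. Second, a patient who improves and then settles is a responder under both rules but can have a different first confirmed date. ORR and DoR are the primary endpoints of Part 2 (protocol 2.2, SAP 2.2.2), and the cohorts are small: protocol 1.2.3.1 reports 15 patients in Part 2A.

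**Working it through.** **Step 1: apply both rules to the same sequences.** Inputs are the sentence and the confirmed rows of Table 6. Each cell gives the best confirmed response and the visit of the first confirmed response of PR or better.

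| Status by visit | Sentence (same or better) | Table 6 read literally |
|---|---|---|
| PR, VGPR | PR, visit 1 | none |
| PR, VGPR, CR | VGPR, visit 1 | none |
| PR, VGPR, CR, PD, PD | VGPR, visit 1 | none |
| PR, VGPR, CR, sCR | CR, visit 1 | none |
| PR, VGPR, VGPR | VGPR, visit 1 | VGPR, visit 2 |
| PR, VGPR, CR, sCR, sCR | sCR, visit 1 | sCR, visit 4 |
| PR, PR, VGPR | PR, visit 1 | PR, visit 1 |

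- ORR and CBR differ in the first four rows, where no category repeats.
- CRR differs only in the fourth row, where a single sCR follows a single CR. In the third row the CR is unconfirmed under both rules.
- In the fifth and sixth rows ORR is the same, but the first confirmed date moves later under the table. TTR lengthens and DoR shortens.

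**Step 2: size of the date shift.** M-protein tests fall on Day 1 of each cycle (Schedules of Activities), and Part 2 cycles are 28 days. If assessments are exactly one cycle apart, a one-visit shift is 28/30.4375 = 0.92 months on the SAP's own divisor. A three-visit shift is 84/30.4375 = 2.76 months. The repeat tests at suspected CR, within 1 to 4 weeks, could shorten these gaps.

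**Step 3: size in ORR.** The number of affected patients is not in the documents, so this is the effect of one hypothetical patient in Part 2A. Each patient is 1/15 = 6.7 points. SAP 8.1.3 names the Wilson interval for binary endpoints, and the protocol's 63.4% (48.1, 76.4) with N=41 reproduces as 26/41 by Wilson. The lower limit is

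[p + z²/2n − z√(p(1−p)/n + z²/4n²)] / (1 + z²/n), with z = 1.96 and n = 15.

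- 9/15 = 60.0%: (0.6000 + 0.1281 − 0.2790)/1.2561 = 0.357.
- 8/15 = 53.3%: (0.5333 + 0.1281 − 0.2831)/1.2561 = 0.301.

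**Step 4: the protocol's planning example.** Protocol 9.3 gives 0.814 for the probability that the true rate is at least 50% after 12/20 responses under a Jeffreys prior. Beta(12.5, 8.5) returns 0.814, so the figure reproduces. With one responder fewer, Beta(11.5, 9.5) returns 0.672. For the combination cohorts, 14/20 against 60% reproduces at 0.818, and 13/20 gives 0.671.

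**The case against.** The best defence is that 8.2.2.8 should be read as a whole. The unconfirmed rows apply only when confirmation was not done or failed requirements that those rows do not state, and the sentence above the table can be taken to supply them. On that reading PR then VGPR is confirmed, and the table is merely terse. This is probably what the authors meant. It also means a reader should not infer that Table 6 sends every single occurrence to an unconfirmed category; the rows do not say so. What survives is that the confirmed rows carry their own stricter definition, and nothing makes them yield to the sentence.

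The ORR effect is also narrow. It needs a patient with no response category on two sequential assessments before progression, new therapy or data cut-off. Assessment every cycle, repeat testing at suspected CR, and a reported median DoR of 11.6 months all make that less likely. This objection stands as to frequency. It does not reach the date shift, which arises in patients who improve and then plateau.

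Finally, SAP 8.1 and 8.2.2 make the efficacy summaries descriptive with no hypothesis test, so no formal threshold is crossed. That is correct.

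The Table 6 footnote on CR and sCR, which waives confirmation by two consecutive assessments, does not settle the matter. The same words in Appendix 3 concern MRD testing.

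**Conclusion.** The inconsistency is real and should be corrected, because it sits in the definition of confirmed response that feeds both Part 2 primary endpoints. A program following Table 6 literally could drop a continuously deepening patient from ORR and CBR, and could move the first confirmed date later in patients who deepen and then plateau. One such patient in Part 2A would be worth 6.7 points of ORR.

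The 9/15 and 8/15 counts are hypothetical: the documents give no Part 2A response rate and no count of patients with this pattern. The date shift assumes one assessment per 28-day cycle.

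A reader might go further and infer that ORR will be undercounted, or that the protocol's 63.4% is too low. The documents do not support either. They do not say which rule was programmed, and the sentence is the likelier intent. Nor does CRR change in the PR, VGPR, CR, PD example. No sample size or stated probability is in error.

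**What to change.** In SAP 8.2.2.8:

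- Reword the sCR, CR, VGPR, PR and MR rows of Table 6 so that each requires that category or better at two or more sequential disease assessments.
- Limit UsCR, UCR, UVGPR and UPR to a status not followed by the same or a better status.
- State that this one rule governs BOR, ORR, CRR, CBR, TTR and DoR.

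The cost is SAP wording. No data collection, visit or sample size changes. If response programs already exist, check which rule they apply and whether any patient's status or first confirmed date differs.

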8.2.2.9. Clinical Benefit Rate (CBR)

A subject with a BOR of sCR, CR (with or without MRD negativity) VGPR, PR, and MR is defined as having Clinical Benefit (CB). The CBR is defined as the percentage of subjects with CB according to the appropriate analysis set. Number and percentage of subjects having CB will be tabulated by treatment group.

Proportion of subjects having minimal residual disease among sCR and CR subjects will be summarized by dose cohorts. The mITT analysis set will be used.

8.2.2.10. Duration of Stable Disease (DoSD)

The DoSD is defined for patients with stable disease as the time from the first documentation of objective stable disease to the first documentation of objective tumor progression or to death due to any cause, whichever occurs first. It will be calculated as follows:

$$\text{DoSD (months)} = [\text{date of event or censoring} - \text{first date of SD} + 1] / 30.4375$$

The censoring rules for DoSD are as described for PFS in [Section 8.2.2.1](#). This analysis will include only participants with confirmed stable disease or better. The DoSD rate at 3, 6, 9, 12 and 18 months will be estimated with corresponding two-sided 95% CIs.

For subjects with no adequate baseline assessment but with post-baseline assessments which can confirm SD, subjects will be censored to first dose date, then we will calculate DoSD= max ((date of event or censoring – first date of SD + 1) , 1). So DoSD will be 1 day instead of negative value.

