Duration of Stable Disease (DOSD) is defined for patients with confirmed stable disease as the time from the first documentation of objective stable disease to the first documentation of objective tumor progression or to death due to any cause, whichever occurs first.

Time to Response (TTR) is defined for patients with confirmed objective response (as defined above in overall response) as the time from the first documentation of objective tumor response.

PF-06863135
C1071001
Final Protocol Amendment 9, 28 March 2023

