Efficacy	
 To evaluate anti-myeloma activity of PF-06863135 as monotherapy and in combination with lenalidomide, pomalidomide, or dexamethasone. 	
 ORR defined using the International Working Group (IMWG) response criteria for multiple myeloma and is the percentage of participants with best overall confirmed BOR of sCR, CR, VGPR, or PR relative to the appropriate analysis set. Time to event endpoints as follows: 
 TTR defined as the time from date of first dose to the first documentation of objective treatment response (PR, VGPR, CR, or sCR, whichever is earlier in participants with BOR of PR, VGPR, CR or sCR). CRR defined as the proportion of subjects with confirmed stringent Complete Response (sCR) and Complete Response (CR). CBR defined as proportion of subjects with a BOR of sCR, CR (with or without MRD negativity) VGPR, PR, and MR. DOR, defined as the time from the first documentation of OR to the first documentation of objective PD of progression, clinical relapse or to death due to any cause, whichever occurs first. DoCR or sCR, defined as the time from the

		
first documentation of complete response to the first documentation of objective progression, clinical relapse or death due to any cause, whichever occurs first.
 
 • DOSD is defined for patients with stable disease as the time from the first documentation of objective stable disease to the first documentation of objective tumor progression or to death due to any cause, whichever occurs first. • PFS, defined as the time from date of first dose to date of first documentation of objective PD of progression, or death due to any cause (progression as defined by IMWG response criteria for PD). • OS, defined as the time from date of first dose to date of death due to any cause. Subjects are censored at the time of last follow-up. • Rate of patients with no MRD (by lab data) after treatment with PF-06863135 using IMWG MRD criteria

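### SAP 8.2.2.10 admits responders to duration of stable disease but starts the clock at an SD date that some of them, and some patients classed as SD, do not have

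*SAP*

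**What the plan says.** SAP 8.2.2.10 opens with a definition: "The DoSD is defined for patients with stable disease as the time from the first documentation of objective stable disease", ending at progression or death. The formula uses the same origin: event or censoring date, minus the "first date of SD", plus 1, divided by 30.4375. The section then sets the analysis population: "This analysis will include only participants with confirmed stable disease or better". It asks for DoSD rates at 3, 6, 9, 12 and 18 months.

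The endpoint table in SAP 2.2 has no 'or better': "DOSD is defined for patients with stable disease as the time from the first documentation of objective stable disease". Neither has Protocol 9.4, where DoSD "is defined for patients with confirmed stable disease as the time from the first documentation of objective stable disease".

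The SD row of Table 6 (SAP 8.2.2.8) adds that a patient with one sCR, CR, VGPR, PR or MR "but no SD response can also confirm SD". It gives no date for such a patient.

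The only date adjustment in 8.2.2.10 is for patients without an adequate baseline, whose negative duration is set to 1 day.

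**The concern.** The population sentence admits MR, PR, VGPR, CR and sCR, while the definition and the formula need a recorded SD date. This has two consequences.

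- Some patients in the set have no start date. The programmer must drop them or choose a date that the SAP does not give.
- Patients who pass through SD on the way to a response are computable, but their time in response is reported as stable disease.

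Two programmers following 8.2.2.10 could therefore produce different Kaplan-Meier curves and different 3- to 18-month rates from the same data, and neither would have departed from the text. SAP section 2 says that substantial differences from the protocol will be identified, and 8.2.2.10 flags none.

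**Working it through.** The documents report no DoSD result, so there is no figure to reproduce. The check applies the stated formula to patient histories that the rules allow.

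**Can a direct responder acquire an SD date later?** No, once the response is confirmed. SAP Appendix 2 keeps a patient in the last confirmed category and bars movement to a lower one.

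**Inputs.** DoSD = (event day − first SD day + 1) / 30.4375, from SAP 8.2.2.10. The histories are assumed, in days with first dose as day 1.

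| Patient | History | DoSD as written (months) |
|---|---|---|
| A | SD d29 and d57, PD d141; best response SD | (141 − 29 + 1)/30.4375 = 113/30.4375 = 3.71 |
| B | SD d29, PR from d57, PD d365 | (365 − 29 + 1)/30.4375 = 337/30.4375 = 11.07 |
| C | PR from d29, PD d365, no SD status | no SD date, not computable |
| D | single unconfirmed PR d29, PD d85, no SD status; SD by the Table 6 rule | no SD date, not computable |

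**What B's figure contains.** SD before PR lasts (57 − 29)/30.4375 = 28/30.4375 = 0.92 months. DoR is (365 − 57 + 1)/30.4375 = 309/30.4375 = 10.15 months. So 10.15 of the 11.07 months is time in response. PFS is 365/30.4375 = 11.99 months.

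**Scale.** Protocol 1.2.3.2 gives a confirmed ORR of 63.4% (95% CI 48.1 to 76.4) in 41 patients at the full dose. 26/41 = 63.4%, and the Wilson interval for 26/41 is 48.1 to 76.4, so the count is 26 responders. The documents do not say how many had an SD status before responding. The number of responders without a start date is therefore between 0 and 26; the others behave like B. The number of patients like D is not given either.

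**The two possible repairs, on the same histories.**

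- *SD only, by best overall response.* A stays at 3.71 months. B and C leave the analysis. D, started at the single response, is (85 − 29 + 1)/30.4375 = 57/30.4375 = 1.87 months.
- *SD or better, from the first such status.* A 3.71, B 11.07, C (365 − 29 + 1)/30.4375 = 11.07, D 1.87 months. C's value equals its DoR, so this measures duration of disease control.

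**The case against.** The strongest defence is that better statuses count as meeting at least SD. SAP 8.2.2.8 lets a response be confirmed by the same or a better one, and Table 6 lets a single better response stand as SD. On that view the first SD date means the first date of SD or better, and only a clarifying clause is missing. The reading is reasonable, but it is written nowhere: both rules concern classification and neither sets a date. It would also make DoSD identical to DoR for a direct responder such as C, which does not fit the endpoint's name or its definition in SAP 2.2 and Protocol 9.4.

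It can also be said that Protocol section 9 allows the SAP to modify the protocol. That stands: departing from Protocol 9.4 is not in itself the error. The defect is the conflict within 8.2.2.10.

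A reader might infer that the protocol already restricts DoSD to patients whose best response is SD, and that the SAP introduced the counting of response time. Protocol 9.4 does not support this. It says confirmed stable disease and runs to progression or death, so a patient with two SD assessments and then PR fits its definition too. The restriction proposed below is a clarification, not a return to existing protocol text.

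A reader might also infer that the clock should start at first dose. That would give everyone a start date, but Protocol 9.4, SAP 2.2 and SAP 8.2.2.10 all start at first documentation of SD.

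**Conclusion.** Wrong as written, with minor consequences. The population sentence conflicts with the definition and formula of its own section. Followed literally, it leaves direct responders and Table 6 single-response patients without a computable duration, and it credits time in response to stable disease for patients who have SD and then respond.

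Two larger conclusions do not follow. A reader might infer that the formula never yields a duration of stable disease; for a patient with best response SD and a recorded SD status it does (patient A). A reader might also take 26 of 41 as the number affected; it is an upper bound on responders without an SD date, and the lower bound is 0.

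DoSD is a secondary endpoint in both parts. SAP 8.2.2 plans no formal testing of efficacy endpoints, and no sample size, dose decision or stopping rule uses DoSD. What changes is the reported DoSD curve and its landmark rates. The monthly figures above rest on assumed histories and show the mechanism, not the expected size in the trial.

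**What to change.** In SAP 8.2.2.10, delete 'or better' and restrict DoSD to patients with best overall response of SD under Table 6. Keep the start at first documentation of SD. For Table 6 single-response patients with no SD status, start at the date of that single response. Identify the best-response restriction as an SAP clarification of Protocol 9.4.

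Alternatively, keep the wider population, start at the first status of SD or better, and rename the endpoint duration of disease control. The definition in SAP 2.2 would then need the same change.

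The cost is SAP wording, best settled before database lock. The drawback of the first option is that the set is smaller and is selected on never having a confirmed response, so it should be reported descriptively only.

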8.2.2.11. Minimal Residual Disease (MRD)

MRD to be summarized as per Appendix 3 if data permits.

Minimal Residual Disease (MRD) (assessed by central lab) negativity rate is the proportion of participants with negative MRD per IMWG sequencing criteria by bone marrow aspirate (BMA) at any time after first dose.

MRD negativity rate is defined as the proportion of participants with negative MRD (assessed by central lab) per IMWG sequencing criteria at any time after first dose of study intervention. MRD negativity will be defined by two thresholds, 10^{-5} and 10^{-6} .

Point estimates of MRD negativity rate will be calculated along with the 2-sided 95% CIs using the Clopper-Pearson method⁵.

MRD negativity rate will also be summarized among participants who achieved CR or sCR with 2-sided 95% CIs.

If data permits, MRD-negativity status at 1-year, 2-year and 3-year from the time of first documentation of MRD-negativity may be summarized by number and percentage among participants who achieved CR or sCR and MRD negativity.

